#### Estimator

The RMET will be estimated as the area under the Kaplan-Meier ‘survival’ curve up to a prespecified point in time (Royston & Parmar, 2013) or in other words, the integral of the survival function over the study period. However, a modeling approach will need to be used here in order to adjust for gender. As the main analysis for time to the *first* 5-point increase in MDS-UPDRS Part III subscale, RMET from Baseline to the last observed event time will be estimated. This will be done by fitting a generalized linear model with a linear link function for the RMET, with gender and age at Baseline as covariates and treatment group as the effect of interest. Further details on this analysis will be given in the SAP.

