To assess neurodegeneration, the biomarker Dopamine Transporter Imaging with Single Photon Emission Computed Tomography (DaT-SPECT) will be used, which is the best-established *in vivo* method to monitor dopaminergic neurodegeneration. It has been reported in the literature that DaT-SPECT results are not impacted (or are only marginally impacted) by using ST (Ikeda et al, 2019). Therefore, DaT-SPECT will be used as an assessment in the study to identify the effect of UCB0599 treatment. Moreover, DaT-SPECT at Screening will allow identification of the relevant target population by identifying patients without evidence of dopaminergic deficit.

Previous studies that have attempted to demonstrate efficacy of non-symptomatic treatments for PD in early-stage populations have failed to show disease modification. Among the reasons for failure, insufficient treatment duration to detect delayed treatment effect and the high variability of disease progression have been identified. An 18-month duration was chosen because it is expected to be sufficient time for UCB0599 to reveal a disease modifying effect and to differentiate from ST.

In addition, the impact of UCB0599 on time-to-initiation and overall intake of ST will be investigated. Since UCB0599 treatment is expected to slow disease progression and disease progression is directly linked to onset of ST, UCB0599 would be expected to delay the time until the study participants require initiating ST, which therefore can be utilized as an event. The treatment duration of up to 18 months means that treatment effects of UCB0599 on the need for initiation of ST will be able to be assessed in the majority of study participants.

As UCB0599 has an additional potential to slow disease progression in the non-motor domain, which prominently encompasses cognitive functioning, there is a need to include instruments which may capture a signal in this area. The Montreal Cognitive Assessments ([MoCA]; Nasreddine et al, 2005) will be used to complete the main assessments, as it covers different cognitive domains. It is available in parallel versions (with only limited training effects and well-established validity in the PD population) and can thus be utilized for longitudinal observations. Furthermore, the MoCA will play a role in Screening, to exclude participants with a pronounced cognitive impairment, which specifically in younger participants could be indicative of a neurodegenerative disorder other than PD.

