4 POPULATIONS FOR ANALYSIS

The following analysis sets will be used:

- *All Study Participants Set (ASPS)*: All study participants who sign the ICF. Treatment assignment in the ASPS will be based on treatment received.
- *Randomized Set (RS)*: All study participants who are randomized. Treatment assignment in the RS will be based on treatment received.
- *Safety Set (SS)*: All randomized study participants who receive at least a partial dose of study medication. Treatment assignment in the SS will be based on treatment received.
- *Full Analysis Set (FAS)*: All randomized study participants who receive at least a partial dose of study medication, have at least 1 post-Baseline assessment. This is *any non-missing* post-baseline assessment, including unscheduled assessments. The FAS will be used for all efficacy analyses, and analyses will be conducted based on randomized treatment. This analysis set will exclude participants who do not meet key inclusion/exclusion criteria (see [appendix 6](#)), these will include criteria related to: age and disease duration at time of informed consent/baseline, Hoehn and Yahr stage at screening, evidence of dopamine transporter deficit (from screening DaT-SPECT) and ST status at screening.
- *Pharmacokinetic Set (PKS)*: All study participants in the Safety Set who have at least 1 observable PK measurement. The PKS will be used for PK analyses and treatment assignment in this analysis set will be based on actual treatment received.

The FAS will be used for all analyses with ICEs and other protocol deviations to be handled according to the approach specified for each estimand (see Sections 1.2). For a given endpoint, the analysis models will exclude any participant with a missing assessment at baseline for that particular endpoint.

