Symptomatic Treatment Status and other ICES

For all summary tables and listings where ST status is used or presented, the assumption is made that once a participant starts ST, they remain on ST for all study visits after their initiation date.

For summary tables that are being presented for participants who are not yet on ST, this means not yet on ST by a particular visit. This means that the number of participants contributing to the summary will differ by visit in the table, as more participants may have initiated ST by the following visit.

For plots that are displayed by ST initiation timing, the following categories will be defined for participants who started ST:

- By month 2 (inclusive);
- between month 2 and 4 (inclusive);
- between month 4 and 6 (inclusive);
- between month 6 and 8 (inclusive);
- between month 8 and 10 (inclusive);
- between month 10 and 12 (inclusive);
- between month 12 and 18 (inclusive);
- not started by 18 months/EOT.

To support the efficacy analyses presented in this section, a (cumulative) summary table presenting the number and percentage of participants with each ICE (see [Section 1.2](#) for a full list of the ICEs defined in this study) will be produced by visit.

Modelling considerations

Baseline covariates

For any analyses adjusting for continuous covariates, these covariates will be mean centered to aid interpretability (the intercept term can be interpreted as the expected value of the response when the dependent variables are set to their means). When mean centering covariates, the calculated mean will be based on the data used for that estimand analysis. All efficacy models will include age at baseline as a covariate. Since this study was randomized stratifying for gender, gender should be included as a covariate in all efficacy models unless explicitly stated otherwise.

As stated in [Section 4](#), for all analyses, a participant should only be included in the model if they have a baseline score for the endpoint being analyzed.

Estimation considerations and Convergence issues

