5.3.1.4 Supplementary approaches

5.3.1.4.1 Supplementary analysis in the absence of ST initiation: de-mediated difference in mean at 12 months

Missing data will be imputed using multiple imputation (MI) according to randomized treatment.

A ‘hypothetical’ handling strategy of ST initiation will be implemented, where all data (up to Month 12) recorded after a participant initiates ST will be corrected using a de-mediation approach.

For further details on the MI and ST de-mediation approaches, see [appendix 5](#).

The population-level summary of interest will be the ST de-mediated difference in target population mean MDS-UPDRS Part I-III sum score at Month 12 as if the participants had not initiated ST between the following treatment arms:

- UCB0599 high dose (360mg/day) and placebo
- UCB0599 low dose (180mg/day) and placebo

ALMEM for longitudinal analysis of covariance (ANCOVA)/repeated measures will be applied to all ST de-mediated data recorded up to Month 12. Treatment, time (visit, categorical) and treatment by time (interaction term between treatment and visit) will be fitted as fixed effects, gender, age at Baseline and Baseline MDS-UPDRS Part I-III will be fitted as covariates. A heterogenous auto-regressive (ARH1) variance-covariance matrix will be fitted to account for the repeated measures within subject.

A summary table presenting the estimated ST de-mediated treatment effects of interest, i.e. difference in means at Month 12 (based on the treatment by time interactions) and corresponding 95% CIs will be produced.

A plot displaying the estimated ST de-mediated means and 95% confidence interval for each treatment group and each time point up to Month 12 will be produced.

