function over the study period. However, a modelling approach will need to be used here so that we can adjust for gender and age at baseline. As the main analysis for time to the *first* 5-point increase in MDS-UPDRS Part III subscale, RMET from Baseline to the last observed event time will be estimated. This will be done by fitting a generalized linear model with a linear link function for the RMET, with gender and age at baseline as covariates and treatment group as the effect of interest. This model will be fitted using the inverse probability censoring weighting (IPCW) method of estimation, this method uses Kaplan-Meier estimation to obtain weights and it has been shown that weighting in this way provides an unbiased estimate for an adjusted survival curve (Calkins, 2018). By default, this approach assumes that the right-censoring mechanism is homogeneous among all participants, which may not be a valid assumption in this study; censoring in the context of this analysis will come from both ST initiation and study termination and it is possible that both may be higher or lower in the UCB0599 arms compared to placebo. This is especially true for ST initiation, if UCB0599 shows signs of efficacy it is likely that a lower number of participants will begin taking ST in these treatment groups. To counter this potential bias, we will obtain treatment group-specific weights by applying the KM estimation method separately to each group (ie, using treatment group as a stratification variable in the model).

A summary table presenting the adjusted difference in RMET of the *first* 5-point increase in MDS-UPDRS Part III subscale between each UCB0599 treatment group and placebo and the corresponding 95% CIs will be produced, this summary will also include the model estimates of adjusted RMET for each treatment group.

To support the interpretation of these analyses, a summary table will be produced showing the number and percentage of study participants who reach this endpoint by treatment group and visit. A listing will also be produced showing date and type of event (ie, 4 options: confirmed first 5-point increase, first 5-point increase followed by ST initiation, ST initiation only, or treatment-related “lack of efficacy” study termination) for each participant, based on the FAS.

Sensitivity analyses

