5.3.2.4.1 Time to ST Initiation

Definitions of endpoints

The participant-level endpoint will be time from Baseline to start of ST or last censored time observation within the 18-month period.

Main analytical approach

Full details on the ICE handling for this estimand can be found in [Section 1.2](#). The main ICEs for this estimand will be study termination and loss to follow up (see details in [Table 1–3](#)).

The population level summary will be the difference in target population restricted mean event time (RMET) up to the last observed event time within the 18-month period between:

- UCB0599 high dose (360mg/day) and placebo
- UCB0599 low dose (180mg/day) and placebo.

In this study, the RMET can be interpreted as the average time until ST initiation within the study period. This summary was chosen as it has been shown to be robust when the proportional hazards assumption does not hold, can be estimated even under heavy censoring, and has an easy clinical interpretation (Royston and Parmar, 2013).

As the main analysis for time to ST initiation, RMET from Baseline to the last observed event time will be estimated. This analysis will use the same modelling approach as described for the MDS-UPDRS Part III subscale time to worsening analysis (see [Section 5.3.2.1.5](#) for further details). By default, this approach makes the assumption that the right-censoring mechanism is homogeneous among all participants, which may not be a valid assumption in this study; censoring in the context of this analysis will come from study termination and it is possible that termination may be higher or lower in the UCB0599 arms compared to placebo. To counter this potential bias, we will obtain treatment group-specific weights by applying the KM estimation method separately to each group (ie, using treatment group as a stratification variable in the model). A summary table presenting the adjusted difference in RMET of ST intake between each UCB0599 treatment group and placebo and the corresponding 95% CIs will be produced, this summary will also include the model estimates of adjusted RMET for each treatment group.

Sensitivity analyses

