Additionally, the RMET will be estimated for each combination of treatment group and gender as the area under the KM “survival” curve up to the last observed event time (ie, without using a modeling approach). A plot of these KM curves will be produced, with the RMET estimates also included in the figure. See [Section 5.3.2.1.5](#) for further details.

Supplementary analyses (Cox regression)

As a supplementary analysis a Cox regression model will be fitted to all observed data since this is the traditional way of modelling time-to-event data. This approach assumes proportional hazards for all individuals and the validity of this assumption will be assessed as detailed in the sensitivity analyses section above. Gender and age at baseline will be included as covariates in the model and treatment group as the effect of interest. A summary table presenting the hazard ratios of ST initiation (UCB0599 high dose vs placebo and UCB0599 low dose vs placebo) and the corresponding 95% CIs will be produced.

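### The restricted-mean model for time to symptomatic treatment adjusts for gender and age only; adding the baseline MDS-UPDRS Part III score is a free improvement with a probably modest gain in precision

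*SAP*

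**What the plan says.** SAP 5.3.2.1.5 (time to Part III worsening, a key secondary estimand) fits a linear-link model for RMET "with gender and age at baseline as covariates and treatment group as the effect of interest", using inverse-probability-of-censoring weights. Protocol 9.3.1.2.2 has the same list: "with gender and age at Baseline as covariates and treatment group as the effect of interest".

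For time to ST, SAP 5.3.2.4.1 states: "This analysis will use the same modelling approach as described for the MDS-UPDRS Part III subscale time to worsening analysis". Its Cox supplement matches: "Gender and age at baseline will be included as covariates in the model and treatment group as the effect of interest". The Part II worsening RMET in 5.3.2.1.7 also points back to 5.3.2.1.5.

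The general rule in SAP 5.3 is "All efficacy models will include age at baseline as a covariate", with gender added because randomization was stratified on it. That rule sets a minimum and does not rule out further covariates.

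Other models do use the baseline value. In the categorical-time MDS-UPDRS model of 5.3.1.4.1, "gender, age at Baseline and Baseline MDS-UPDRS Part I-III will be fitted as covariates". The Part I, II and III versions, MoCA (5.3.2.2.2) and DaT-SPECT (5.3.2.3.2) follow the same pattern, and the slope models carry baseline in the response. The optional analyses with extra prognostic covariates cover only the primary slope and the Part III slope (5.3.1.3, 5.3.2.1.2).

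**The concern.** SAP 1.1 says that "disease progression is directly linked to onset of ST", and Step 1 of the g-estimation in SAP 6.5.5 regresses ST initiation on the current MDS-UPDRS score. If the current score drives ST, the baseline score should carry much of that information: in SAP Table 3-1 the between-participant intercept variance is 154.0 out of 185.1. SAP 3.1 also reports an intercept-slope correlation of 0.43 in PPMI, so participants with higher scores tended to progress faster.

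With a linear link and randomized arms, adding a baseline covariate leaves the marginal difference in RMET as the target. It can only help to the extent that the covariate is prognostic. At stake is some width of the time-to-ST interval, plus any chance difference in severity between arms, because randomization balances gender alone (Protocol 6.3).

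**Working it through.** **1. The plan's own figure.** No power or precision figure is given for any RMET analysis. The only figure to reproduce is 143 per arm for the primary slope. From Table 3-1: σ² = 154.0 + 31.1 = 185.1; ρ = 154.0/185.1 = 0.832; r_τ = 0.43/185.1 = 0.00232; Δ² = 0.27²/185.1; N₁Var(T) = 85.57. Then n = 2 × [(1 − ρ) + r_τ × 85.57] × 2.56² / (85.57 × Δ²) = 142.7, which rounds up to 143. This confirms the reading of Table 3-1 and does not test the RMET models.

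**2. What a covariate buys.** In a linear-link model the variance is multiplied by about 1 − R², where R² is the share of variance in restricted event time explained by the covariate. The SE is multiplied by √(1 − R²), and the equivalent sample size is 143/(1 − R²).

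| R² | SE multiplier | Equivalent n per arm |
|---|---|---|
| 0.02 | 0.990 | 146 |
| 0.05 | 0.975 | 151 |
| 0.10 | 0.949 | 159 |
| 0.20 | 0.894 | 179 |

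**3. R² for time to ST, large-sample simulation.** There were 400,000 participants with Table 3-1 components, independent intercept and slope, and a log-linear ST hazard in the current true score. The hazard ratio (HR) per SD and the share starting ST by 18 months are assumptions.

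| ST by 18 months | HR 1.3 | HR 1.6 | HR 2.0 |
|---|---|---|---|
| 45% | 0.017 | 0.050 | 0.100 |
| 60% | 0.023 | 0.068 | 0.130 |
| 75% | 0.030 | 0.086 | 0.160 |

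An independent repeat with 200,000 participants agreed to within 0.001. With the documented correlation of 0.43, R² was 0.021-0.194, and 0.087 in the central case (HR 1.6, 60%). The central SE reduction is therefore 1 − √(1 − 0.068) = 3.5% to 1 − √(1 − 0.087) = 4.4%.

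**4. Time to ST at trial size.** This simulation had 143 per arm, 18 months, arm-specific Kaplan-Meier censoring weights, an assumed 15% dropout at 12 months and 600 replicates. ST by 12 months was set to 20% (the planning value in SAP 3.2) or 58% (PPMI, same section). Part III variance components are not stated. They were scaled by 0.496, the ratio implied by 90% power at 0.19 points/month with 143 per arm: 143 × 0.19²/(2 × 2.56²) = 0.394, against 31.1/85.57 + 0.43 = 0.793 for the sum score. The models compared were treatment alone and treatment plus baseline score; gender and age were not simulated.

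| ST by 12 months | Correlation | HR 1.0 | HR 1.5 | HR 2.0 |
|---|---|---|---|---|
| 20% | 0 | 0.999 | 0.992 | 0.954 |
| 20% | 0.43 | 1.002 | 0.998 | 0.942 |
| 58% | 0 | 1.003 | 0.945 | 0.892 |
| 58% | 0.43 | 1.004 | 0.963 | 0.908 |

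Entries are the SE with baseline divided by the SE without. R² was 0.028-0.195 for HR 1.5-2.0 and 0.000 for HR 1.0.

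**5. Part III worsening, same simulation.** The event was a confirmed 5-point rise or ST initiation, whichever came first. Over all twelve scenarios R² was 0.001-0.055 and the SE ratio 0.972-1.005. A high observed baseline makes a 5-point rise less likely through regression to the mean, but makes ST more likely and, with correlation 0.43, progression faster. In the composite these effects largely cancel. SAP 5.3.2.1.5 treats ST initiation as an event but later names it as a source of censoring; the simulation used the event definition.

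**The case against.** The strongest objection is that nothing in the documents gives the size. The HRs are assumed, the gain vanishes at HR 1.0, and the sentence in SAP 1.1 is about progression, not baseline level. Inclusion criterion 7a selects participants not expected to need ST within 6 months, which may weaken the baseline-to-ST relation and was not modelled. All of this stands. It limits the size but not the direction, because SAP 6.5.5 itself models ST initiation on the score.

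It is also fair that gender and age form a consistent convention: the Cox, logistic, relative-risk and negative binomial models all follow it, and the Amendment 3 summary shows that wider adjustment was considered and cut back. No reason is given, however, why the event models should lack a baseline score that the continuous models use.

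The change is not purely wording. The protocol lists the same covariates. Time to ST has no baseline value of its own, and SAP 4 says that "the analysis models will exclude any participant with a missing assessment at baseline for that particular endpoint", so a Part III covariate could drop participants unless a rule prevents it. These costs are real but small.

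A reader might infer that the key secondary Part III worsening estimand has materially wider intervals than necessary. Step 5 does not support that. A reader might also infer bias. Under randomization, omitting the covariate does not bias the estimator, and chance imbalance is already reflected in its interval.

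**Conclusion.** The omission is confirmed for the time-to-ST RMET model and for the model it reuses. Adding the baseline score is a free improvement. Its absence is not a defect that threatens the trial's conclusions, in an exploratory study that makes no power claim for any RMET endpoint.

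For time to ST, the baseline score explains roughly 2-20% of the variance if the HR is 1.3-2.0 per SD of current score. The SE is then about 1-11% smaller by the variance rule, and about 3-4% in the central case; at trial size with low ST uptake and HR 1.5 the simulated gain was below 1%. For Part III worsening the reduction is 0-3%, so the case there rests on consistency with the other models and on accounting for chance imbalance. Part II worsening was not assessed. All ranges depend on the assumed prognostic strength.

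**What to change.** Before database lock:

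- **Time to ST (SAP 5.3.2.4.1):** add the mean-centred baseline MDS-UPDRS Part III score to the RMET model. Use the latest pre-dose value under SAP 5.1.2.1.5, and a simple rule such as mean imputation if it is missing. State that the missing-baseline exclusion in SAP 4 does not extend to this covariate.
- **Part III worsening (5.3.2.1.5) and Part II worsening (5.3.2.1.7):** pre-specify the baseline Part III and Part II score respectively, without claiming a material precision gain.
- **Optional:** mirror the covariate in the Cox supplement, noting that the hazard ratio then becomes conditional on baseline score. The ST-intake logistic and relative-risk models (5.3.2.4.2) may be aligned in the same way.
- **Record:** list the change in SAP Appendix 2, because the protocol names gender and age only.

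The cost is one covariate per model and a SAP amendment. No new data are needed. Adding the covariate after unblinding would look data-driven.

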1.2 Intercurrent events

The tables below cover all planned efficacy analyses, except for sensitivity analyses.

The strategies/approaches for handling ICEs will be as follows:

- *Treatment Policy*: all data will be included in the analysis, regardless of whether the participant remains on the assigned investigational treatment or discontinued. This will reflect the treatment effect regardless of the ICE.
- *Hypothetical*: data will be modified to mirror its value had an ICE not happened (under some hypothetical conditions). One such hypothetical condition is that the ICE occurred completely at random. In this case, all post-ICE data are set to missing (removed) and imputed under the assumption of missing at random (MAR). This strategy can be applied to ICEs which are considered uninformative with respect to the effect of interest. As a default approach, this strategy will be applied to any occurrence of an ICE affecting the existence of measurements and maximum likelihood (ML) imputation will be used for continuous gaussian-distributed endpoints where a linear mixed effect model is used for analysis (Schafer and Graham, 2002). Alternative imputation approaches will also be considered for ICEs which are considered informative with respect to the effect of interest, under the assumption of missing not at random (MNAR), such as reference-based imputation (RBI) approaches (Carpenter, Roger & Kenward, 2013) for continuous endpoints and non-response imputation (NRI) where missing responder status is imputed as non-response for binary endpoints (Floden and Bell, 2019), as well as causal inference methods (Lasch et al., 2022). This approach will reflect the treatment effect had the ICE not occurred.
- *Composite*: ICE data will be incorporated into the endpoint being analyzed. This approach will be used for the MDS-UPDRS Part II/III time to worsening analyses; a composite endpoint of time to worsening or time to ST initiation will be used as ST initiation is considered representative of a negative outcome.

Table 1-2: Overview of handling strategies for ICEs, ICE-like protocol deviations and study termination or loss to follow-up for MDS-UPDRS estimands

		MDS-UPDRS Part I-III sum score and Part I/II/III subscales	
Estimand	Primary, key secondary and secondary	Key secondary	Secondary and supplementary
Handling ICE (ST initiation)	In the absence of ST initiation	ST initiation as part of the response	Regardless of ST initiation

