Population summary measure	For Part I-III sum score: Difference in slope of progression at 12 months (primary) and difference in mean at 12	For Part III subscale: Difference in RMET (time to confirmed first 5-point increase or ST	For Part I-III sum score: Difference in mean at 12 and 18 months (supplementary)

Table 1–2: Overview of handling strategies for ICEs, ICE-like protocol deviations and study termination or loss to follow-up for MDS-UPDRS estimands

	
and 18 months (key secondary and supplementary)^a
 
For Part III subscale: Difference in slope of progression at 12 months (key secondary)
 
For Part III subscale and Part III ePD subscore^a: Difference in mean at 12 and 18 months (key secondary)
 
For Part I/II subscale: Difference in mean at 12 and 18 months (secondary)
	
initiation) within 18 months (key secondary)
 
For Part II subscale: Difference in RMET (time to confirmed first 3-point increase or ST initiation) within 18 months (supplementary)
	
For Part I/II/III subscales: Difference in mean at 12 and 18 months (supplementary)

ICE & ICE-like protocol deviations			
ST initiation (Non-MAO-B Inhibitors) ^c	Hypothetical (set to missing & impute all post ICE visit data – MAR/ML)	Composite (ICE is part of the endpoint)	Treatment policy (Include post-ICE data)
ST initiation (MAO-B Inhibitor) ^c	Hypothetical (set to missing & impute all post ICE visit data – MAR/ML)	Composite (ICE is part of the endpoint)	Treatment policy (Include post-ICE data)
Treatment discontinuation (Lack of efficacy or AE)	Treatment policy (Include post-ICE data)	id	id
Treatment discontinuation (Other causes)	Treatment policy (Include post-ICE data)	id	id
Important ICE-like protocol deviations			
with long-term impact ^d	Hypothetical (set to missing & impute all post ICE visit data – MAR/ML)	Hypothetical (set to missing & treat as right-censored (non-event) at time of initial IPD)	id
With short-term impact ^d	Hypothetical (set to missing & impute single post-ICE visit data – MAR/ML)	Hypothetical (ignore)	id

Table 1–2: Overview of handling strategies for ICEs, ICE-like protocol deviations and study termination or loss to follow-up for MDS-UPDRS estimands

Death or serious injury (all causes)	Actual missing: impute all post ICE visit data – MAR/ML	Actual missing: treat as right-censored (non-event) at time of termination	id

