5.3.2.1.5 MDS-UPDRS Part III subscale: time to worsening within 18 months

Definitions of endpoints

The participant-level endpoints will be the time from Baseline to the participant's *first* 5-point increase in MDS-UPDRS Part III subscale (or to last observed time prior to ST initiation) within the 18-month period, where the 5-point increase is confirmed at the next visit record, or ST initiated before the next visit record.

Main analytical approach

Full details on the ICE handling for this estimand can be found in Section 1.2. The main ICE will be initiation of ST, this will be handled using a "composite" strategy where initiation of ST is part of the endpoint definition. Study termination and loss to follow up related to treatment "lack of efficacy" will be handled by using non-responder imputation and be considered an event as part of the composite handling strategy. All other occurrences of study termination and loss to follow up will be right-censored, i.e., analysis only takes account of events which occurred within the observed duration.

The population level summary will be the difference in target population restricted mean event time (RMET) up to the last observed event (or last observed time prior to ST initiation) between:

- UCB0599 high dose (360mg/day) and placebo
- UCB0599 low dose (180mg/day) and placebo

In this study, the RMET can be interpreted as the average time to the *first* 5-point increase in MDS-UPDRS Part III subscale within the study period or to initiation of ST, whichever comes first. This summary was chosen as it has been shown to be robust when the proportional hazards assumption does not hold, it can be estimated even under heavy censoring, and has an easy clinical interpretation (Royston and Parmar, 2013).

The RMET can be estimated as the area under a Kaplan-Meier (KM) survival curve up to a pre-specified point in time (Royston & Parmar, 2013) or in other words, the integral of the survival

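### The SAP's estimator paragraph for Part III time to worsening treats start of symptomatic treatment as censoring, against the composite strategy set for the same endpoint

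*SAP*

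**What the plan says.** SAP Section 5.3.2.1.5 opens its analytical approach with "Full details on the ICE handling for this estimand can be found in Section 1.2". In Section 1.2 the composite strategy is described with the words "This approach will be used for the MDS-UPDRS Part II/III time to worsening analyses". The ST rows of Table 1-2 for this endpoint read "Composite (ICE is part of the endpoint", and the table's summary measure is the RMET to a confirmed 5-point rise or ST start. Section 5.3.2.1.5 itself interprets the RMET as the average time to the 5-point increase "within the study period or to initiation of ST, whichever comes first". Its planned listing of event types has ST initiation alone as one of four kinds of event. Protocol Sections 9.3.1.2.2 and 9.5 also specify composite handling.

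The paragraph of Section 5.3.2.1.5 that sets out the inverse-probability-of-censoring-weighted model says something else: "censoring in the context of this analysis will come from both ST initiation and study termination". The next sentence begins "This is especially true for ST initiation, if UCB0599 shows signs of efficacy", and the two together are the reason given for estimating the Kaplan-Meier weights separately by arm.

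Some other wording also leans towards censoring. The endpoint definition in Section 5.3.2.1.5, and its Part II counterpart in Section 5.3.2.1.7, run time to the increase "or to last observed time prior to ST initiation". The endpoint definition in protocol Section 9.3.1.2.2 calls the ST time censored. SAP Table 1-1, protocol Table 9-1 and the population summary in protocol Section 9.3.1.2.2 label the estimand as being in the absence of ST, which the notes to both tables define as censoring data after ST.

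**The concern.** For one endpoint, ST start cannot be both the event and a censoring time. The conflicting sentence stands where a programmer looks to learn what counts as censoring in the weighted model. The parallel paragraph for time to ST (SAP Section 5.3.2.4.1) names study termination only.

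If ST were coded as censored, the analysis would estimate time to worsening with ST starters removed at ST start, which is not the composite the plan defines. SAP Section 1.1 links progression directly to ST onset, so that censoring would also be informative; weighting by arm does not correct for this within an arm. The unweighted Kaplan-Meier sensitivity analysis would not reveal the problem if it used the same status variable. The Part II 3-point analysis in Section 5.3.2.1.7 takes its model from this section and inherits the conflict.

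**Working it through.** **Which passages make ST an event, and which make it censoring**

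- Event: Section 1.2 text; Table 1-2 summary measure and ST rows; the strategy statement, the RMET interpretation and the event listing in Section 5.3.2.1.5; protocol Sections 9.3.1.2.2 (strategy) and 9.5.
- Censoring: the two sentences in the estimator paragraph of Section 5.3.2.1.5; the endpoint definition in protocol Section 9.3.1.2.2.
- The right-censoring rows of Table 1-2 for this endpoint are long-term important protocol deviations ("treat as right-censored (non-event) at time of initial IPD"), death or serious injury, and termination or loss to follow-up for causes other than lack of efficacy. ST is not among them.

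**Size of the difference between the two codings**

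The documents give no power, event count or expected RMET for this estimand, so there is no stated figure to reproduce.

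Inputs: horizon 18 months (Section 5.3.2.1.5). ST start by Month 12, ps: 20% (planning value) or 58% (228/391 in PPMI), both from SAP Section 3.2. Worsening by Month 12, pw: 30-60%, an assumption that is not in the documents. Hazards are assumed constant and independent.

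- lw = -ln(1 - pw)/12 and ls = -ln(1 - ps)/12
- ST as event: RMET = (1 - exp(-18(lw + ls)))/(lw + ls)
- ST as censored: RMET = (1 - exp(-18 lw))/lw

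Example with pw = 40%, ps = 20%: lw = 0.04257, ls = 0.01860, sum 0.06116. Event: (1 - 0.3326)/0.06116 = 10.91 months. Censored: (1 - 0.4648)/0.04257 = 12.57 months.

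The last three columns give the active-minus-placebo difference when the drug cuts the named hazard by 30%. Each cell is event / censored, in months.

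| ps | pw | Placebo RMET | ST only | Worsening only | Both |
|---|---|---|---|---|---|
| 20% | 30% | 12.02 / 13.94 | 0.53 / 0 | 0.87 / 1.07 | 1.46 / 1.07 |
| 20% | 40% | 10.91 / 12.57 | 0.46 / 0 | 1.10 / 1.36 | 1.64 / 1.36 |
| 20% | 50% | 9.78 / 11.19 | 0.39 / 0 | 1.30 / 1.60 | 1.78 / 1.60 |
| 20% | 60% | 8.63 / 9.78 | 0.32 / 0 | 1.46 / 1.78 | 1.87 / 1.78 |
| 58% | 30% | 8.24 / 13.94 | 1.28 / 0 | 0.49 / 1.07 | 1.89 / 1.07 |
| 58% | 40% | 7.60 / 12.57 | 1.12 / 0 | 0.63 / 1.36 | 1.91 / 1.36 |
| 58% | 50% | 6.95 / 11.19 | 0.97 / 0 | 0.76 / 1.60 | 1.90 / 1.60 |
| 58% | 60% | 6.26 / 9.78 | 0.81 / 0 | 0.86 / 1.78 | 1.87 / 1.78 |

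**Relaxing independence.** A simulation tied the ST hazard to Part III change. It used a placebo slope of 0.19/0.35 = 0.543 points per month from SAP Section 3.3, with an assumed slope SD of 0.45 and residual SD of 3.5-4.5. The gap was smaller but remained: placebo RMET 9.3-10.0 (event) against 10.4-10.8 (censored) at 20% ST, and 6.7-7.9 against 10.1-10.5 at 58%.

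**Dating the ST event.** Using the last bimonthly visit before ST in place of the ST date shortens placebo RMET by about 0.2 month at 20% ST and 0.5-0.6 month at 58%. It moves the treatment difference by less than 0.1 month.

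**The case against.** The strongest reply is that the plan already settles the coding. Section 5.3.2.1.5 defers to Section 1.2, which is clear, and nothing in the estimator paragraph tells anyone to set ST to a non-event. The sentence is rationale: arm-specific weights remain usable under composite coding because termination may also differ by arm. The protocol's censoring wording has little force, since SAP Section 1 lets the protocol apply only where the SAP does not specify. The planned event-type listing would expose miscoding. ST start also has its own analyses in Sections 5.3.2.4.1 and 5.3.2.4.2. A drug acting on ST alone is an unlikely scenario, and the study is exploratory with no multiplicity adjustment.

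Most of this stands, and it limits the point to a correction of wording. It does not remove it: a sentence that names the censoring sources of a weighted estimator should be right.

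A reader might infer more. One inference is that the estimand is undefined, or that ST will in fact be censored; Section 1.2 and Table 1-2 do not support that. Another is that ST would be an event and also enter the weights; that needs a separately programmed censoring indicator, and no section specifies one. A third is a bias of known direction; the table shows that the direction depends on where the drug acts.

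**Conclusion.** The conflict is real and worth correcting, but the intended composite coding is recoverable from Section 1.2.

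Under constant independent hazards with 30-60% worsening by Month 12, placebo RMET is 8.6-12.0 months (event) against 9.8-13.9 (censored) at 20% ST, and 6.3-8.2 against 9.8-13.9 at 58% ST. Across both ST rates, the treatment difference is 0.3-1.3 months against 0 for a 30% cut in ST hazard only, 0.5-1.5 against 1.1-1.8 for worsening only, and 1.5-1.9 against 1.1-1.8 for both. The worsening rates and the hazard cuts are assumptions; 58% is an observational rate, not the trial's.

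The primary estimand and the separate ST estimands are not affected. The wording on the last observed time before ST is a minor dating point. The label about absence of ST is loose but does not itself set the event indicator.

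**What to change.** Keep the composite strategy and make these changes before the study team is unblinded, so that the coding is not chosen with results in view.

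1. SAP Section 5.3.2.1.5, estimator paragraph: remove ST initiation as a censoring source and delete the sentence that follows. Keep the arm-specific Kaplan-Meier weights. State that they use only the right-censoring rows of Table 1-2 (termination or loss to follow-up not due to lack of efficacy, long-term important protocol deviations, death or serious injury) plus end of follow-up.
2. SAP Sections 5.3.2.1.5 and 5.3.2.1.7: wherever time is said to run to the last observation before ST, use the date of ST initiation, counted as an event. The Part II analysis then inherits the corrected model through its cross-reference.
3. Optional: relabel the Table 1-1 bullet as composite, and align protocol Table 9-1 and Section 9.3.1.2.2 at the next amendment.

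No entry in SAP Appendix 2 is needed, because the protocol already specifies composite handling. The cost is a few sentences of SAP text, with no new data and no change of model.
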